After randomization, subjects will undergo a Trial Phase lasting up to 10 days to determine subject's response to assigned treatment group. Temporary or permanent leads and an external neurostimulator (ENS) will be used during the Trial Phase. Subjects will evaluate the assigned treatment group based on pain intensity under optimal parameters. Those who have a "successful Trial Phase" (defined as a 40% or greater pain reduction from Baseline

in their back pain) will proceed to permanent implantation of a SCS system to evaluate the assigned treatment group.

The implanted neurostimulator (INS) will be activated within 14 days after surgical procedure and SCS therapy will be delivered for the next 12 months. Activation of the device marks the initial time point for effectiveness evaluation of the study therapies after implantation. Assessments of pain intensity, use of medication and adverse events will be made at 1 month following Device Activation. At 3, 6, 9, and 12 months after Device Activation, subjects will be assessed for pain intensity, adverse events, extent of disability, use of medication, and quality of life (EuroQol EQ-5D-5L). Patient Global Impression of Change, and subject satisfaction will also be recorded at 3, 6, 9 and 12 months after Device Activation. Subjects have the option to crossover to the other arm after completing the 6 months visit (up to 30 days after completing the 6 month visit).

Figure 1 summarizes the sequence of study-related assessments, procedures, and activities.

[figure not shown]

Figure 1. Study Flowchart

B.6.2. Consent/Enrollment

Medical records of all subjects deemed by the Investigator to be potential candidates for the study will be de-identified and sent to a sponsor designated physician for pre-screening. De-identified medical records should include detailed medical and surgical history of the pain condition under study as well any information about comorbidities. Any imaging studies (such as MRI, CT, X-ray) should be included for evaluation of the study candidate. Once the site has received confirmation that subject may be an appropriate candidate for this study, the site may proceed with the eligibility process. This de-identified pre-screening process assists in reducing unnecessary visits for subjects that would not be eligible for this study.

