At the end of the Trial Phase, subjects will be assessed for pain intensity under optimal therapy parameters. Anterior-posterior (AP) and lateral X-ray imaging may be done at the end of the Trial Phase. The subject will be assessed for adverse events and medication usage.

Those who have a "successful Trial Phase" (defined as a 40% or greater pain reduction from Baseline in their back pain) will proceed to permanent implantation of a SCS system to evaluate the assigned therapy, and permanent implantation of the Intellis™ SCS system will be scheduled. A threshold of 40% for the Trial Phase was predetermined as the minimum pain reduction that warrants consideration of a permanent implant and an

opportunity to achieve a 50% pain reduction as defined in the Individual Subject Success criterion (see Section B.7.3.).)

Data from subjects who did not achieve 40% or greater pain reduction in back and do not receive permanent implantation will be carried forward toward the primary and secondary endpoints. These subjects will exit the study after being followed up for two weeks after explant of the leads to assess adverse events.

B.6.8. Permanent Device Implant (0-60 days from end of successful Trial Phase)

As described in section B.6.7, subjects who underwent a successful trial of the assigned SCS therapy and who agreed to continue into the next stage of the study will proceed to permanent implantation stage.

Permanent percutaneous leads will be placed in the epidural space at a vertebral level based on the subject's pain condition and pain pattern as described in the Intellis™ Physician Implant Manual. The INS will be implanted by a trained physician according to standard practice and following the Physician Implant Manual for the device. Anterior-posterior (AP) and lateral X-ray imaging will be obtained. Standard practice of a study site for prophylactic pre-surgery antibiotics and post-surgery pain medications will be followed). Subjects will be assessed for adverse events and medication usage.

B.6.9. Device Activation (0-14 days following Permanent Implant)

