The following secondary endpoints do not have an associated hypothesis, and no significance level will be assigned to statistical tests that may be performed. Analysis of these endpoints will be based on a repeated measures approach that accounts for within subject correlation. Treatment group status for the repeated measures models will be based on treatment status at the current time point (i.e. it will be based on treatment status incorporating potential crossover, not necessarily the original randomized assignment).

- Comparison of Back Pain Treatment Success (responder rate), measured as subjects with at least a 50% reduction in Back Pain VAS, between test and control
- Comparison of mean change from Baseline in Back Pain VAS, between test and control

B.9.2.3 Additional Data

- Comparison of Leg Pain Treatment Success (responder rate), measured as subjects with at least a 50% reduction in Leg Pain VAS, between test and control for subjects with baseline leg pain VAS score ≥ 5
- Comparison of mean change from Baseline in Leg Pain VAS, between test and control for subjects with baseline leg pain VAS score ≥ 5
- *Satisfaction with Therapy*: Subject Satisfaction will be compared between test and control
- *Patient Global Impression Change*: The Patient Global Impression of Change from Baseline to follow-ups at 3-, 6-, 9- and 12-month visits after device activation will be compared between the treatment groups.

- *Oswestry Disability Index (ODI)*: The changes in ODI from Baseline to 3-, 6-, 9- and 12-months will be summarized as continuous variables and compared between the treatment groups.
- *Quality of Life*: The changes in the EQ-5D-5L instrument from Baseline to follow-ups at 3-, 6-, 9- and 12-months will be summarized as continuous variables and compared between the treatment groups.
- *Paresthesia Questionnaire*: Questions about the paresthesia will be used at 3-, 6-, 9-and 12-month visits and compared between test and control

B.9.2.4 Handling of Missing Data

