Missing data will be minimized by rigorous follow-up and investigator and site training. Additionally, for subjects who do not have a successful Trial Phase, results from the Trial Phase will be utilized for the primary endpoint as described in Section B.7.2. Effectiveness Assessment Definitions. Any other data will be imputed via Multiple Imputation. Additionally, sensitivity analyses for missing data will be performed. Unless otherwise specified, all other analyses will be based on the evaluable data with no imputation.

Details on imputation will be provided in a separate statistical analysis plan.

C. Risk Analysis

C.1. Description and Analysis of All Increased Risks to Subjects

Spinal Cord Stimulation (SCS) Risks:

DTM-SCS programming approach will be used with commercially available, FDA approved Intellis™ SCS system within approved indications for use. Anticipated potential adverse events resulting from the study are expected to be in line with adverse events already documented for SCS using a Standard programming approach.

There are known risks associated with the use of any SCS system. Known risks are associated with the implant procedure, the stimulation, the implanted device (not associated with stimulation) and external devices such as the charger and remote control. These are typical of commercial SCS systems. Subjects will be informed of these anticipated risks in the study consent process.

Risks of Surgery

Implanting a neurostimulation system has risks similar to spinal procedures, including spinal fluid leak (spinal fluid collection under the skin), headaches, swelling, bruising, bleeding, infection, or paralysis.

Subjects on anticoagulation therapy may be at higher risk for problems after surgery such as hematomas that could result in paralysis.

Spinal Cord Stimulation Risks

The implantation of a spinal cord stimulation system involves risks that are similar to other spinal procedures. In addition to those normally associated with surgery, implantation or use of a neurostimulation system includes, but is not limited to the following risks:

- Allergic or immune system response to the implanted materials
- Infection
- Lead or neurostimulator erosion through the skin or migration
- Leakage of cerebrospinal fluid
- Loss of pain relief may return patients to their underlying pain condition
- Persistent pain at the neurostimulator site

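### The 3-month ODI, EQ-5D-5L, PGIC and satisfaction comparisons omit randomized subjects who failed the Trial Phase, so they are conditional on response to the assigned treatment

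*Combined protocol and SAP*

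**What the plan says.** Randomization follows Baseline and precedes the Trial Phase (B.6.1, B.6.5). Implantation, and every visit after it, requires a successful Trial Phase, "defined as a 40% or greater pain reduction from Baseline" in back pain, achieved on the assigned treatment (B.6.1, B.6.7).

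For what is measured at that point, B.6.7 says: "At the end of the Trial Phase, subjects will be assessed for pain intensity under optimal therapy parameters." It adds adverse events, medication use and optional imaging. Of subjects who fall short and are not implanted it says: "These subjects will exit the study after being followed up for two weeks after explant of the leads to assess adverse events." Table 1 agrees. Its End Trial Phase column has VAS, medication, adverse events and, for failures, Study Completion, but nothing for ODI, EQ-5D-5L, PGIC or satisfaction.

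B.6.7 carries the data of these subjects forward to the primary and secondary endpoints. B.9.2.4 says that for them "results from the Trial Phase will be utilized for the primary endpoint". It then says "Any other data will be imputed via Multiple Imputation", and closes the rule with "Unless otherwise specified, all other analyses will be based on the evaluable data with no imputation". Finally: "Details on imputation will be provided in a separate statistical analysis plan."

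ODI, EQ-5D-5L, PGIC and satisfaction are neither primary nor secondary endpoints. They are additional data (B.7.5, B.9.2.3). Even so, they are to be compared by arm. For ODI: "The changes in ODI from Baseline to 3-, 6-, 9- and 12-months will be summarized as continuous variables and compared between the treatment groups."

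**The concern.** The Trial Phase acts as a filter after randomization, and the treatment under comparison helps decide who passes. For back pain the plan deals with this: trial failures count as non-responders (Synopsis, Primary Endpoint) and B.7.2 gives them an efficacy assessment at the end of the Trial Phase. For disability and quality of life it does not. Failures have a baseline but no later value, and the default rule drops them.

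A 3-month ODI or EQ-5D-5L result presented as a comparison of treatment groups would then compare responders to one programming approach with responders to the other. The arm with more failures loses more of its poor outcomes. The result would stand beside a back-pain result that does count failures, with nothing to tell the reader that the two rest on different sets of subjects.

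**Working it through.** **1. Who contributes a 3-month value.**
- Passed the Trial Phase and implanted: ODI and EQ-5D-5L at Enrollment/Baseline and after activation; PGIC and satisfaction after activation.
- Failed the Trial Phase: ODI and EQ-5D-5L before treatment only; PGIC and satisfaction never.
- Control subjects counted as failures for use above 250 Hz still go on to implant (B.4), so they keep these visits. The gap concerns pain-based failures.
- The mITT set (B.7.1) includes failures, but a subject with no measurement and no assigned value adds nothing to an analysis of observed data.

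**2. What the attrition figure shows.** B.5.5.2 allows 25% combined attrition: 100 / 0.75 = 133.3, so 134 against the stated 135; and (135 - 100) / 135 = 25.9%. The planning figure reproduces, but it is not a Trial Phase failure rate. It mixes non-completion of the Trial Phase with exits before month 3. A subject who completes the Trial Phase with under 40% relief has a primary assessment under B.7.2, and so may sit among the 100 rather than among the 35. The number of failures could be smaller or larger than 25%.

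**3. Simple model (assumed values).** Let the mean ODI change be -m in implanted subjects of both arms and 0 in failures, with failure rates fT (test) and fC (control).
- Implanted-only difference: -m - (-m) = 0, whatever the failure rates.
- Difference over all trialed subjects: -(1 - fT)m + (1 - fC)m = -(fC - fT)m.

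With m = 20 and trial success of 90% against 75%: 0.90 x (-20) = -18.0 and 0.75 x (-20) = -15.0. The difference is -3.0, but the planned analysis shows 0. With the rates exchanged, the test arm is 3 points worse and the analysis again shows 0.

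Points in favour of test over all trialed subjects, at a mean failure rate of 25%:

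| Failure, test / control | m = 10 | m = 20 | m = 30 | Implanted-only |
|---|---|---|---|---|
| 25% / 25% | 0 | 0 | 0 | 0 |
| 20% / 30% | 1 | 2 | 3 | 0 |
| 15% / 35% | 2 | 4 | 6 | 0 |
| 10% / 40% | 3 | 6 | 9 | 0 |

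**4. Model with correlated outcomes (assumed values).** Let trial pain relief be normal with SD 1 and means +d/2 (test) and -d/2 (control). A common cut-off k gives the stated mean failure rate, and ODI improvement has correlation r with relief. The full difference is r x d. The implanted-only difference is r x [d + h(k - d/2) - h(k + d/2)], where h(a) is the standard normal density at a divided by the upper tail beyond a.
- Mean failure 25%, d = 0.5, r = 0.5: failures 17.2% / 32.8%; 0.250 SD becomes 0.135 SD (54%).
- Mean failure 15%, same d and r: failures 9.4% / 20.6%; 0.250 SD becomes 0.162 SD (65%).
- Over d = 0.3 to 0.8 and r = 0.5 to 0.7, the implanted-only comparison keeps 54-55% of the full difference at 25% mean failure and 64-66% at 15%.

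Both models pull the comparison toward no difference when the test arm has fewer failures.

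**5. Whether unequal failure is plausible.** B.1 reports mean back-pain relief during trialing of 68% with DTM-SCS and 43% with Conventional SCS in a 20-subject feasibility study. The second mean lies close to the 40% gate. That study is small and its rates of passing a 40% gate are not given, so it makes equal failure an unsafe assumption and no more.

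**6. Leg pain.** VAS is taken at End of Trial (B.8.1, Table 1) and covers back and leg (B.8.2). A value therefore exists for failures. What is missing is a rule that brings it into the 3-month leg-pain comparison.

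**The case against.** The strongest reply is that nothing confirmatory depends on these measures. They carry no hypothesis or margin, B.8.2 sets no success criterion beyond the primary endpoint, and the primary endpoint already counts failures. This stands, and it limits the weight of the point.

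A second reply is that the scope is partly a choice. PGIC is defined at visits after device activation, and satisfaction is naturally asked of people who have the implant. For those two, honest labelling goes most of the way. For ODI and EQ-5D-5L, which have a pre-treatment value and are presented as arm comparisons, the argument is weaker.

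A third is that the multiple-imputation sentence, or the separate analysis plan, may cover the gap. Read broadly, that sentence contradicts the no-imputation sentence that closes the rule. Nor would it help much: no failure has any post-baseline ODI or EQ-5D-5L, so imputed values would be extrapolated from subjects who passed. A separate plan, not among the documents here, could assign values but could not recover questionnaires never collected. The final handling is uncertain; the missing visits are not.

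Three stronger readings are tempting and lack support. A reader might infer that about a quarter of subjects will be missing as trial failures; step 2 shows that the 25% is neither that rate nor a bound. A reader might infer that a true difference could reverse; the models show loss or attenuation, not reversal. And a reader might treat leg pain as equally unmeasured, which step 6 rules out.

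**Conclusion.** The point holds for ODI and EQ-5D-5L, and as a matter of labelling for PGIC and satisfaction. Following the schedule and default rule as written gives 3-month comparisons conditional on passing a post-randomization response filter, while describing them as comparisons of the treatment groups.

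The size cannot be stated from the documents, which give no failure rate overall or by arm and no outcomes for failures. In the simple model the lost difference is the gap in failure rates times the mean improvement, and with equal rates there is no bias in that example. In the correlated model roughly half to two thirds of the difference survives. Both rest on assumed inputs. The primary conclusion is untouched, so this is a change worth making before subjects exit, not a threat to the trial's main result.

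**What to change.** 1. **Collection (Table 1, B.6.7).** Obtain ODI and EQ-5D-5L, and also PGIC and satisfaction, from Trial Phase failures at End of Trial or at the existing two-week post-explant contact. B.9.1 already allows phone, mail or email.
2. **Analysis (B.9.2.3).** Add a 3-month between-arm comparison of ODI and EQ-5D-5L on the mITT set. For the subjects whom B.7.2 defines (trial failures, and those declining implant for insufficient relief), use the collected value, or no change from Baseline if it is absent, with a sensitivity analysis on that assumption. For leg pain, use the observed End of Trial leg VAS, as B.7.2 does for back pain. Treat subjects not implanted for other reasons as missing data.
3. **Reporting.** Label implanted-only results, including PGIC and satisfaction, as conditional on implantation, and report trial failures by arm.

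The cost is a few questionnaires and some analysis-plan wording. Failures would be measured earlier than month 3, and after explant if the later contact is used, which should be stated with the result. Within-arm improvements will look less favourable than in implanted subjects alone. Treatment, eligibility, sample size and the primary analysis do not change.

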The sample size estimate to determine primary endpoint is based on the primary objective of demonstrating non-inferiority of the test group to the control group at 3

months. Established methods were followed in determining the non-inferiority criteria and the related sample size estimate

- Test basis: Farrington-Manning binomial test for non-inferiority
- Estimated responder rate of 70% in the test group and 50% in the control group
- Significance level, alpha, of 0.05 one-sided
- Statistical power = approximately 90% or greater
- Non-inferiority margin of 10%
- Randomization: 1:1

Based on these assumptions, a minimum of 50 randomized and trialed subjects per treatment group (100 total) are required.

B.5.5.2 Overall Sample Size and Enrollment

Based on the primary endpoint requirement, a minimum of 50 subjects per treatment group are required (100 total). To account for a combined estimated attrition of 25% for subjects that do not complete the Trial Phase, and subjects that exit study before the 3-month primary endpoint visit, approximately 135 subjects would need to be randomized and trialed.

To account for 46% attrition prior to randomization (including subject ineligibility after signing the informed consent and subject dropout), it is estimated that a total of up to 250 subjects would need to be enrolled in the study.

B.5.6. Study Duration

This study is expected to last approximately 32 months. Enrollment of subjects is expected to last 18 months. Subjects who are expected to complete the study will commit to it for approximately 14 months. This consists of Baseline assessments, up to 10 days of trial stimulation, and 12 months of treatment following implantation and activation of the device.

B.5.7. Interim Administrative Analyses

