A 10% margin has been previously used in a similar study.¹⁶ Meeting the statistical threshold for this test based on a 10% margin should produce clinically acceptable results.

B.9.2.2 Secondary Analyses

The following *secondary endpoints* will be evaluated:

- If the primary efficacy endpoint in the test group is found to be non-inferior to that in the control group, then a secondary endpoint will evaluate whether the proportion of subjects who achieve a 50% improvement in their back pain VAS score at 3 months in the test group is superior to that in the control group. A superiority test based on the difference in proportions will be performed based on the following null hypothesis, with a one-sided p-value of 0.05 or less considered evidence of statistical significance.

H_0 : The proportion of subjects (P) who achieve a 50% improvement in their back pain VAS score at 3 months in the Test group is less than or equal to that in the Control group.

$$P_{\text{Test}} \leq P_{\text{Control}}$$

H_1 : The proportion of subjects (P) who achieve a 50% improvement in their back pain VAS score at 3 months in the Test group is greater than that in the Control group.

$$P_{\text{Test}} > P_{\text{Control}}$$

- Change in mean VAS will be evaluated with two-sample t-test of non-inferiority in means with a 0.65 cm margin at 3 months.

H_0 : The change (C) in subject's VAS pain intensity score relative to baseline at the Primary Efficacy Assessment in the Test group is inferior to that of subjects in the Control group (active control).

$$C_{\text{Test}} \geq C_{\text{Control}} - 0.65 \text{ cm}$$

H_1 : The change (C) in subject's VAS pain intensity score relative to baseline at the Primary Efficacy Assessment in the Test group is not inferior to that of subjects in the Control group (active control).

$$C_{\text{Test}} < C_{\text{Control}} - 0.65 \text{ cm}$$

The non-inferiority margin of 0.65 cm was selected based on a previous study of a similar therapy against traditional SCS¹⁶. In that study, the experimental therapy showed a 4.9 point improvement while traditional SCS showed a 3.6 point improvement for a difference of 1.3 points. Taking 50% of this treatment effect yields the margin of 0.65.

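### The gated 3-month superiority test and the VAS t-test default to evaluable data, while the primary test of the same endpoint imputes missing scores

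*Combined protocol and SAP*

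**What the plan says.** Section B.9.2.4 has three steps. Subjects with an unsuccessful Trial Phase contribute their Trial Phase result to the primary endpoint, as B.7.2 describes. Other missing data are multiply imputed. Then: "Unless otherwise specified, all other analyses will be based on the evaluable data with no imputation". The section also promises missing-data sensitivity analyses, without saying which endpoints they cover, and leaves imputation details to a separate analysis plan that is not among the documents.

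Section B.9.2.2 makes superiority conditional on non-inferiority: "a secondary endpoint will evaluate whether the proportion of subjects who achieve a 50% improvement in their back pain VAS score at 3 months" is higher in Test than in Control, at one-sided 0.05. It adds a VAS t-test with a 0.65 cm margin, whose hypotheses are written at the Primary Efficacy Assessment. Neither test has a missing-data rule of its own. B.7.1 puts primary and secondary endpoints on the same mITT set: randomized subjects who complete the Trial Phase.

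On unsuccessful trials, B.6.7 says the data "will be carried forward toward the primary and secondary endpoints", whereas B.9.2.4 mentions only the primary endpoint. B.7.2 places the Primary Efficacy Assessment at the end of the Trial Phase both for these subjects and for those who decline the implant because relief was insufficient.

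**The concern.** The superiority test uses the same responder variable, visit and analysis set as the non-inferiority test that opens it. Yet an implanted subject with no month-3 score is imputed in one and absent from the other. The report could then carry two different responder differences for one endpoint, with the formal superiority claim resting on the one that leaves subjects out.

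Those losses could well be related to relief. B.6.18 and B.6.19 provide for explant, withdrawal for adverse events, and subjects considering withdrawal because the therapy is not working. B.9.1 withholds mailed questionnaires from subjects who, for example, have turned the device off. The trial is open-label (B.5.4), so the pattern may differ by arm. At stake are the error rate and power of the superiority claim and the estimate in the VAS comparison. Study success is not at stake: B.8.2 rests it on the non-inferiority test alone.

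**Working it through.** **1. The plan's own sample size.** Inputs from B.5.5.1: "Estimated responder rate of 70% in the test group and 50% in the control group"; a margin of 10 percentage points; "Significance level, alpha, of 0.05 one-sided"; 1:1 allocation. Farrington-Manning power at 50 per arm is 92.7% (exact enumeration also 92.7%), and 45 per arm would give 90%. The stated "Statistical power = approximately 90% or greater" is met. B.5.5.2: 100/(1 − 0.25) = 133.3, so 134 against about 135 stated; 250 × (1 − 0.46) = 135. These figures hold, and the fix does not change them.

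**2. Superiority with complete data.** At 70% versus 50% and one-sided 0.05, power is 65.7% at 50 per arm and 76.8% at 67 per arm (135/2, rounded down).

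**3. Error of the evaluable-case superiority test.** Assumptions, none of them from the documents: 67 per arm all open to loss, true response 50% in both arms, month-1 and month-3 scores bivariate normal with correlation 0.7, and 90% of losses from the poorer half at month 1.

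- Response rate in the poorer half: 0.5 − arcsin(0.7)/π = 0.253. In the better half: 0.747.
- Response rate among those lost: 0.9 × 0.253 + 0.1 × 0.747 = 0.303.
- Response rate among those retained at loss L: r(L) = (0.5 − 0.303 L)/(1 − L), giving 0.510, 0.522, 0.535 and 0.549 at L = 5%, 10%, 15% and 20%.
- Approximate error: 1 − Φ(1.645 − Δ/SE), where Δ is the difference in r(L) between arms and SE² is the sum over arms of r(1 − r)/[67(1 − L)].

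Example, 20% Test versus 10% Control: Δ = 0.0274, SE = √(0.2476/53.6 + 0.2495/60.3) = 0.0936, Δ/SE = 0.293, error 1 − Φ(1.352) = 8.8%.

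| Loss, Test / Control | Δ | SE | Error by formula | Error by simulation |
|---|---|---|---|---|
| 15% / 15% | 0 | – | 5.0% | 5.0% |
| 10% / 5% | 0.0115 | 0.0898 | 6.5% | 6.3–6.6% |
| 15% / 5% | 0.0244 | 0.0911 | 8.4% | 8.1–8.6% |
| 20% / 10% | 0.0274 | 0.0936 | 8.8% | 9.0–9.6% |
| 5% / 10% | −0.0115 | 0.0898 | 3.8% | 3.8–3.9% |
| 5% / 15% | −0.0244 | 0.0911 | 2.8% | 3.0% |

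Ranges span separate simulation runs. With 3,000 runs the Monte Carlo standard error at 5% is √(0.05 × 0.95/3000) = 0.4 points.

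**4. The same data with multiple imputation using month-1 VAS.** Error is 4.2–4.9% at 20% versus 10% loss and 4.3–4.5% at 15% versus 5%. In 5.6% of runs at 20% versus 10%, the evaluable-case test declared superiority and the imputed test did not. At a true 70% versus 50% with 5% Test and 15% Control loss, power is 63–65% on evaluable cases and 75–76% with imputation. Imputation does well here partly by construction, because loss was made to depend mainly on month-1 pain.

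**5. Loss that depends on the month-3 outcome itself.** Suppose 10% are lost in each arm, all non-responders in Test but at random in Control. The evaluable rates are 0.5/0.9 = 55.6% and 50%, and the error is 15.2%; with the pattern reversed it is 1.2%. This is an extreme case. It shows that equal loss rates protect the test only if the dependence on response is also alike in both arms, and that imputation under missing at random is not a complete answer.

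The VAS t-test cannot be sized in this way, because no standard deviation is given.

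**The case against.** The restriction of imputation to the primary test is inferred. The imputation sentence names no endpoint, the default yields to anything specified elsewhere, and details are deferred. That stands as a caution. However, if imputation covered every endpoint the default would govern nothing, and B.9.2.2 does not override it.

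A reader might infer four stronger things, which the documents do not support.

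- *Trial Phase failures drop out of the superiority test, so the claim rests on a response-selected subset.* B.6.7 carries them into the secondary endpoints, and B.7.2 gives them, and those who decline the implant for insufficient relief, an observed end-of-trial outcome for the Primary Efficacy Assessment. The wording in B.9.2.4 needs aligning, but it does not say that these results serve the primary endpoint alone.
- *A quarter of subjects, 135 × 0.25 ≈ 34, are handled differently in the two tests.* The sentence in B.5.5.2 begins "To account for a combined estimated attrition of 25% for subjects that do not complete the Trial Phase" and adds exits before month 3. Non-completers are outside mITT in both tests, and no split is given.
- *Gated testing requires one data set for both tests.* It requires only that each test be valid at its own level. The issue is bias in the second test, not an alpha cost of the gate.
- *The bias favours Test.* The plan expects Control to respond less well, so heavier Control loss is at least as plausible; that makes the test conservative and costs power.

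It is also fair that B.9.2.4 promises sensitivity analyses and B.7.1 adds supportive ITT and Per-Protocol analyses. Neither fixes which result carries the superiority claim.

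**Conclusion.** The point holds in a limited form. On the natural reading, two tests of one responder endpoint in one analysis set treat missing month-3 scores differently, and the VAS t-test inherits the same default. The subjects affected are mainly those lost between a successful Trial Phase and month 3.

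Bias in the superiority test requires losses that depend on relief and differ by arm. Under the assumptions in step 3, moderately heavier Test loss raises a nominal 5% error to between about 6% and 10%, equal loss leaves it near 5%, and heavier Control loss lowers it and reduces power by about 11 points (for example 76% − 65%) relative to imputation. The loss rates, the correlation and the share of losses from poor responders are all assumed. Non-inferiority and study success are unaffected. The change should be made because the rule is already written, the claim it governs is formal, and the remedy is nearly free.

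**What to change.** In B.9.2.4, replace the general default for these two tests with a rule to this effect: the 3-month superiority test and the VAS t-test use the same mITT set, the same handling of unsuccessful Trial Phases and of implant refusals for insufficient relief (B.6.7, B.7.2), the same imputed data sets and the same missing-data sensitivity analyses as the primary non-inferiority test. In addition:

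- Include End-of-Trial and month-1 VAS in the imputation model; both are already collected (B.8.1).
- Name a non-responder or tipping-point analysis among the sensitivity analyses, because imputation under missing at random does not remove all response-dependent loss.
- Keep the evaluable-data result as a sensitivity analysis.
- Align the reference to the primary endpoint in B.9.2.4 with B.6.7, which covers primary and secondary endpoints.

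The cost is one paragraph and a little extra programming. The imputed data sets are needed for the primary test anyway, and the sample size does not change.
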